9.3 Exclusion Criteria

1. Pregnant or lactating women
2. Expected need for major surgery during trial.
3. Current or previous diagnosis of malignant disease, except for basal cell or squamous cell carcinoma of the skin with complete excision and clear borders or adequately treated in situ carcinoma of the cervix.
4. Acute infections identified during screening that require antibiotics. These subjects would be eligible to participate following resolution of infection before Day 1 visit within the allowed 46 days screening period. The subject will re-screen if it extends beyond the allowed 46 days screening period. See more details of information about the 46 days screening window period in section 9.4 Screening and Randomization, line 9-10.
5. Chronic infections such as hepatitis B, hepatitis C, HIV or Tuberculosis.
6. Current use of cyclophosphamide or having received cyclophosphamide within the last year.
7. Prior history of hemorrhagic cystitis or hematuria while receiving cyclophosphamide that could not be explained by other causes.
8. Current use (within 3 months) of tocilizumab, rituximab, belimumab, intravenous gammaglobulin or other biologic.
9. History of poor compliance with medical care, study visits and/or medication use.

10. Receipt of any investigational new drug or device within 30 days prior to screening or 5 half-lives of the agent (whichever is longer), or any investigational new drug with known long-term effects.
11. Pioglitazone is not recommended in patients with symptomatic heart failure. Patients with current heart failure (NYHA class II, III or IV) and/or a left ventricular ejection fraction of <45% by echocardiogram at screening will be excluded.
12. Significant impairment of major organ function (lung, heart, liver, kidney) or any condition that, in the opinion of the Investigator, would jeopardize the subject's safety following exposure to the study drug.
13. Known hypersensitivity to TZDs
14. Serum hepatic transaminase levels > 2 times upper normal limit, or clinical evidence of active liver disease at screening. The only exception is patients with confirmed non-alcoholic fatty liver disease (NAFLD) where pioglitazone has been reported to have a therapeutic role.
15. Diagnosis of DM or meeting DM criteria at screening visit, as established by new classification criteria⁹⁶: Patients with diabetes are excluded because diabetes by itself will induce profound changes in endothelial function and we want to assess the effects of PPAR agonists in vascular risk beyond changes in insulin resistance.
16. Known latex allergy for EndoPAT test
17. Patients with severe Raynaud's phenomenon, history of finger ulcers or finger gangrene will not undergo Endopat testing.
18. Patients with severe SLE at baseline, as quantified as SLEDAI-2K >20.
19. Patients with active lupus nephritis or active CNS lupus at baseline even if SLEDAI-2K <20. Active disease will be considered as CNS or renal disease that require aggressive immunosuppression. Active CNS disease will be diagnosed based on clinical presentation and physical exam, exclusion of other conditions that could explain symptomatology and, when warranted, ancillary tests (imaging) that support the diagnosis.

Patients that are not on induction therapy for lupus nephritis and have chronic (more than 6 months), stable proteinuria <750 mg/gram in protein: creatinine ratio but otherwise considered to have no evidence of active lupus nephritis (e.g. no cellular casts and stable serum creatinine < 2 mg/dL) over the last 6 months, will be included in the study.

In selected patients with potentially confounding clinical factors, consults will be requested to help clarify the nature of any underlying renal disease that may affect inclusion.

20. Postmenopausal women who have not undergone a DEXA scan over the last year will undergo a DEXA scan at screening. Patients with a better than -2.5 will be included. Postmenopausal women who have undergone a DEXA scan during the last year and have a T score better than -2.5 will be included without repeating the DEXA scan prior to enrollment. If the T score is worse than -2.5, they will be excluded from participating unless the subject is willing to begin appropriate treatment for osteoporosis by Visit Day 1. Postmenopausal

women who have undergone a DEXA scan during the last year, have a T score worse than -2.5 and are not on bisphosphonates or other appropriate therapy will be excluded.

Study Visits and Procedures

Table 3: Study Visits and Procedures

Procedure	Screen	Baseline	Month 1	Month 3	Month 5	Month 6	Month 8	Unscheduled visit
Consent and Randomization. Eligibility Questionnaire	X							
Medical History, Physical Exam including vital signs, SLEDAI-2K	X							
Presenting Symptoms-Abbreviated Medical History		X	X	X	X	X	X	X
Physical Exam including vital signs		X	X	X	X	X	X	X
BILAG 2004, SLEDAI-2K ,PGA, SF36		X		X	X		X	
Blood Draw: insulin, glucose, lipids, EPCs, C3, C4, autoAbs, piHDL, cytokines, CRP, ESR , Aim 3 labs, Acute care panel, Lymphocyte Phenotyping TBNK, lipoprotein profile, Urinalysis (includes microscopic), p/c ratio.		X		X	X		X	X
Blood Draw: safety labs (CBC, LFTS, pregnancy tests in women of childbearing potential)		X	X	X	X	X	X	X
Screening labs and imaging. Blood draw: (pregnancy test, lipids, glucose, LFTs, CBC, Anti-ds-DNA, C3, C4, Urinalysis (includes microscopic), p/c ratio, Infectious disease	X							

testing), Echocardiogram (if it has not been obtained within the last 6 months) and DEXA scan (postmenopausal women without DEXA scan in the last year)								
Vascular function Studies		X		X	X		X	
Dispense Drug		X			X			
AE Review			X	X	X	X	X	X
Drug Accountability				X			X	
Health lifestyle Counseling (PRN)		X		X	X		X	
Urine analysis	X						X	X
PET-CT (subset of patients)		X		X				

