9.4 Screening and Randomization

Subjects will review and sign informed consent document, and medical history, physical exam, disease activity (SLEDAI-2K), screening labs and echocardiogram will be performed.

Echocardiogram will not be performed if patient is rescreened within 6 months and previous result is normal or if patient had normal Echocardiogram within 6 months prior to screening.

Routine laboratory data obtained within 30 days of the screening visit under the natural history protocol 94-AR-0066 can be used for screening. Screening labs will include infectious disease testing for HIV, Hepatitis B, Hepatitis C and Tuberculosis if they have not been obtained within the last 6 months. As mentioned above, postmenopausal women without a DEXA scan in the last year will undergo a DEXA scan to assess eligibility. The window between screening and baseline must be less than 46 days, otherwise subjects will need to be rescreened regarding labs. Inclusion/Exclusion Criteria will be signed off based on screening labs and assessment. Patients who meet these criteria will be randomized to a sequence of active drug followed by placebo, or placebo followed by active drug in a 1:1 allocation ratio. Randomization and drug/placebo allocation will be done by the NIH clinical center research pharmacy after screening visit.

We will test Urinalysis (includes microscopic) on Screening and Month 8 visits on all patients. If patients have evidence of microscopic hematuria > 20 RBCs/uL(excluding normal menstruation cycle) it will be repeated twice at one month (+/- 7 days) intervals and if RBCs

are consistently more than 20 RBCs/uL then Urology consult will be placed. The following algorithm will be put in place, per recommendations by the Urology service at NCI:

1. Question patient about macroscopic hematuria > 20 RBCs/uL times 3 results.
 - a. If YES → Urology consult → Cytology
 - i. If abnormal cytology → Cystoscopy → FISH @ Mayo Labs for genetic changes for bladder cancer detection
 - ii. If normal cytology → Nothing

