- An increased incidence of bone fracture was noted in female patients taking TZDs. During a mean follow-up of 34.5 months, the incidence of bone fracture in females was 5.1% (44/870) for pioglitazone versus 2.5% (23/905) for placebo. This difference was noted after the first year of treatment and remained during the course of the study. No increase in fracture rates was observed in men treated with pioglitazone 1.7% (30/1735) versus placebo 2.1% (37/1728). Given the short duration of the trial, we will not assess the effect of this drug on bone metabolism. Given that the mechanism of bone fractures with TZDs is considered different than the one associated with corticosteroid use, we will not change inclusion/exclusion criteria based on medication use. In female patients, attention will be given to assessing and maintaining bone health according to current standards of care and in communication with treating rheumatologist. As mentioned in the exclusion criteria, we will exclude postmenopausal women who have a DXA scan showing a T score worse than -2.5, unless they are willing to begin a bisphosphonate by visit day 1.
- As mentioned above, there have been data suggesting an increase in bladder cancer in diabetics that have been on TZDs for > 2 years. Given the short duration of this trial, no significant concerns are present. Nevertheless, we will exclude patients who have received cyclophosphamide over the last year, whoever developed hemorrhagic cystitis,

or those with a previous history of bladder cancer, or with a history of hematuria not explained by another cause.

Overall, given the short duration of exposure to pioglitazone (3 months), we do not expect repercussions on bone health, bladder or adverse CV outcomes.

12.2.2.7 Echocardiogram:

No side effects are associated with echocardiogram.

12.2.2.8 DXA scan:

The exposure to radiation is minimal from this procedure. No side effects are otherwise expected and this will only be performed in postmenopausal subjects that have not undergone a DXA scan over the last year.

12.3 ADVERSE EVENT AND UNANTICIPATED PROBLEM REPORTING:

The Principal Investigator will be responsible for detecting, documenting, and reporting AEs and SAEs in accordance with the protocol, IRB requirements, and federal regulations.

12.3.1 Definitions:

12.3.2 Adverse Event:

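### Section 12.2.2.6 says unexplained haematuria excludes a patient, but criterion 7 in section 9.3 excludes it only when it occurred on cyclophosphamide

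*Combined protocol and SAP*

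**What the plan says.** Section 12.2.2.6 (Study Drug) addresses bladder cancer and names four groups the trial will exclude: cyclophosphamide in the past year, haemorrhagic cystitis at any time, previous bladder cancer, and patients "or with a history of hematuria not explained by another cause". The last item stands on its own and carries no cyclophosphamide condition.

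In section 9.3, the only numbered criterion that names haematuria is criterion 7: "Prior history of hemorrhagic cystitis or hematuria while receiving cyclophosphamide that could not be explained by other causes". Two others might reach such a patient. Criterion 12 covers "any condition that, in the opinion of the Investigator, would jeopardize" the patient's safety on study drug. Criterion 19, on active nephritis and CNS disease, adds that in selected patients "consults will be requested to help clarify the nature of any underlying renal disease that may affect inclusion".

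Section 9.4 makes the 9.3 list operative: "Inclusion/Exclusion Criteria will be signed off based on screening labs and assessment". It also schedules urinalysis for all patients at Screening and Month 8. If a non-menstrual count exceeds 20 RBCs/uL, "it will be repeated twice at one month (+/- 7 days) intervals", and persistently high counts go to Urology. On timing it says: "The window between screening and baseline must be less than 46 days, otherwise subjects will need to be rescreened regarding labs".

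**The concern.** The risk section describes a protection that the eligibility list does not deliver. Staff who sign off eligibility work from 9.3. Someone judging the trial's safety from 12.2.2.6 would believe that all unexplained haematuria is excluded. The same patient could be handled differently depending on which section is consulted, and one whom the safety section excludes could be randomised with no criterion breached.

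What is at stake is a safety exclusion for a drug whose long-term use the plan itself links to bladder cancer. It is not the validity of any comparison.

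A smaller question follows from 9.4: nothing there ties a high screening count to the start of dosing.

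**Working it through.** **1. The four exclusions in 12.2.2.6 against 9.3**

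| Excluded according to 12.2.2.6 | Counterpart in 9.3 | Agree? |
|---|---|---|
| Cyclophosphamide in the past year | Criterion 6 | Yes |
| Haemorrhagic cystitis, ever | Criterion 7 | Yes, unless the cyclophosphamide phrase is read as qualifying cystitis too |
| Previous bladder cancer | Criterion 3 (malignancy, with skin and cervix exceptions) | Yes; 9.3 is wider |
| Unexplained haematuria, any setting | Criterion 7, on cyclophosphamide only | No |

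The grammar of criterion 7 leaves it unclear whether the cyclophosphamide phrase qualifies cystitis. On either reading it limits haematuria.

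**2. Who falls in the gap**

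A patient with unexplained haematuria that did not occur on cyclophosphamide, with no malignancy history, whom the investigator does not exclude under criterion 12. Haematuria attributed to nephritis is explained under both sections, so those patients are not in the gap. The plan gives no prevalence, so no count can be derived.

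**3. Timing in 9.4 (secondary)**

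Inputs from 9.4: two repeats, each at one month ± 7 days; baseline before day 46, so day 45 at the latest. Section 9.4 does not say how long a month is, so both 30 and 28 days are shown.

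Day of third count = 2 × (month ± 7):
- 30-day month: 2 × 30 = 60, range 2 × 23 = 46 to 2 × 37 = 74.
- 28-day month: 2 × 28 = 56, range 2 × 21 = 42 to 2 × 35 = 70.

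Nominally, then, the third count comes after the latest baseline. How much blinded drug or placebo precedes it depends on section 9.5.1. There, an abnormal baseline lab that needs repeating defers the first dose by up to 4 weeks, and dosing starts if the result has improved or normalised. Table 3 includes urinalysis among the baseline labs, so this hold can apply.

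- Baseline on day 45, full hold: first dose on day 45 + 28 = 73. Exposure before the nominal third count is 0, and at most 74 − 73 = 1 day.
- Baseline on day 45, no hold: 60 − 45 = 15 days (46 − 45 = 1 to 74 − 45 = 29). With 28-day months, 56 − 45 = 11 days (0 to 70 − 45 = 25).
- Earlier baseline: the full hold ends before the nominal third count if baseline falls before day 60 − 28 = 32 (or day 56 − 28 = 28).

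These figures describe a gap in the instructions. They do not show that any patient is harmed.

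**The case against.** The best defence is that 9.3 is the operative list and 12.2.2.6 only summarises it in a discussion of risk. On that view the difference is loose drafting that touches very few people. Criterion 12 lets the investigator exclude anyone of concern, the screening urinalysis is available before sign-off, criterion 19 allows consults, and section 10.1 item 6 allows discontinuation for unacceptable risk. The plan also regards bladder risk over so short an exposure as not a significant concern. Section 6.6 supports this with a hazard ratio of 1.03 (0.84-1.26) under 12 months and a number needed to harm of 20,903, both in type 2 diabetes.

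Most of this stands, and it limits the size of the point. It does not reconcile the sections. 12.2.2.6 states a fixed exclusion, whereas criterion 12 is discretionary and does not name haematuria.

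Two stronger readings are tempting. A reader might infer that 9.4 and 9.5.1 contradict each other, because a third count that is lower but still above 20 calls for Urology under one and allows dosing under the other. They do not: 9.4 says when to refer, 9.5.1 says when to dose, and both can be followed on the same day.

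A reader might also infer that dosing must wait for the full work-up. The documents do not say so. The algorithm follows Urology advice and also runs at Month 8, when treatment is over, so it is partly surveillance. Whether a delay of about two months is worthwhile at this level of risk is open to debate.

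**Conclusion.** The mismatch between 12.2.2.6 and criterion 7 is real and worth correcting. Following 9.3 as written can enrol a patient whom the safety section says is excluded, with only investigator discretion in between. This rests on reading the final item in 12.2.2.6 as independent of cyclophosphamide, which its place in the list supports.

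The consequence is modest. The number affected is unknown and probably small, the cited hazard ratio for short use is close to 1, and no endpoint, power or alpha changes. That hazard ratio comes from patients with type 2 diabetes, so applying it to SLE is an assumption.

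The timing gap in 9.4 is minor. It merits a clarifying sentence at most.

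**What to change.** Reword criterion 7 along these lines: *Prior history of hemorrhagic cystitis, or history of hematuria (whether or not on cyclophosphamide) not explained by another cause such as lupus nephritis, menstruation, infection or stones; hematuria that has been evaluated and cleared by Urology does not exclude.* Carry the same wording, including the clearance clause, into 12.2.2.6 so that the edit does not create a new mismatch. Agree with Urology what counts as cleared. The 9.4 algorithm ends at "If normal cytology → Nothing", so it should be stated whether that result is clearance.

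Optionally, add to 9.4 that a screening count above 20 RBCs/uL is reviewed against the reworded criterion 7 before the first dose. A mandatory hold until all three counts and the Urology work-up are complete should be added only if the investigators and Urology want it.

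Cost: short text changes and one decision with Urology. A few patients become ineligible or need a Urology opinion. Enrolment is counted from consent (section 9.1) and the 100 places include screen failures (section 8), so anyone excluded after consent uses one place. With up to 75 completers intended, the margin for all screen failures and withdrawals is 100 − 75 = 25 places.

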9.4 Screening and Randomization

Subjects will review and sign informed consent document, and medical history, physical exam, disease activity (SLEDAI-2K), screening labs and echocardiogram will be performed.

Echocardiogram will not be performed if patient is rescreened within 6 months and previous result is normal or if patient had normal Echocardiogram within 6 months prior to screening.

Routine laboratory data obtained within 30 days of the screening visit under the natural history protocol 94-AR-0066 can be used for screening. Screening labs will include infectious disease testing for HIV, Hepatitis B, Hepatitis C and Tuberculosis if they have not been obtained within the last 6 months. As mentioned above, postmenopausal women without a DEXA scan in the last year will undergo a DEXA scan to assess eligibility. The window between screening and baseline must be less than 46 days, otherwise subjects will need to be rescreened regarding labs. Inclusion/Exclusion Criteria will be signed off based on screening labs and assessment. Patients who meet these criteria will be randomized to a sequence of active drug followed by placebo, or placebo followed by active drug in a 1:1 allocation ratio. Randomization and drug/placebo allocation will be done by the NIH clinical center research pharmacy after screening visit.

We will test Urinalysis (includes microscopic) on Screening and Month 8 visits on all patients. If patients have evidence of microscopic hematuria > 20 RBCs/uL(excluding normal menstruation cycle) it will be repeated twice at one month (+/- 7 days) intervals and if RBCs

are consistently more than 20 RBCs/uL then Urology consult will be placed. The following algorithm will be put in place, per recommendations by the Urology service at NCI:

1. Question patient about macroscopic hematuria > 20 RBCs/uL times 3 results.
 - a. If YES → Urology consult → Cytology
 - i. If abnormal cytology → Cystoscopy → FISH @ Mayo Labs for genetic changes for bladder cancer detection
 - ii. If normal cytology → Nothing

9.5 Study Visits

9.5.1 *Baseline visit and 5-month +/- 7 days (post-washout) visit*

- a. Baseline visit will include medical history. The baseline and 5-month (post-washout) visits will consist of a physical exam, and blood draw for biomarkers (Table 3). SF-36, PGA, disease activity (BILAG 2004, SLEDAI-2K) and vascular measurements will be determined and subjects will be issued a 3-month supply of blinded study drug or placebo with instructions. The first week of each treatment arm, patients will take two 15 mg capsules of pioglitazone daily (30 mg total daily dose) and, if no significant side effects develop (primarily fluid retention), will increase to three 15 mg capsules (45 mg total daily dose). Subjects will be instructed to follow the same titration for the placebo arm. Patients will be called prior to increasing the dose to 45 mg to question patients about rapid weight gain (>5 pounds in a week), significant edema or other side effects. Patients will be called 1-2 weeks after increasing dose to 45 mg daily to assess tolerability. If 45 mg dose is not well tolerated but the 30 mg dose is well tolerated, dose will be decreased back to 30 mg daily for duration of trial. PET/CT exams will be performed in 15 patients initially randomized to placebo and 15 patients initially randomized to pioglitazone and the investigators will be blinded to this. PET/CT studies will only be performed at baseline and month 3. Subjects can opt out of the PET/CT scan and still participate in the study. Patients will be asked to participate at baseline until we reach 15 patients/group. If a patient is found to have an acute infection at the baseline visit, they will be given antibiotics and their next visit will be scheduled for no more than 4 weeks later, at which time they will start the study medication. We will repeat only baseline clinical labs at this extra visit; we will not repeat PET/CT, vascular function studies or research sample collection. If a patient has an abnormal lab result at the baseline visit that requires a repeat, the patients next visit will be scheduled no more than 4 weeks later, at which time if the abnormal lab has improved or normalized they will

start the study medication. We will not repeat PET/CT, vascular function studies or research sample collection. If any subjects are enrolled in our Natural History of SLE Protocol (94-AR-0066) and have undergone a research-indicated PET/CT scan as part of that study within the 6 months prior to their baseline visit, we will use that data for their baseline values and will only perform the PET/CT scan at the month 3 visit.

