8 STUDY DESIGN AND METHODS

This will be a single-center, randomized, double-blind, placebo-controlled, crossover, proof-of-concept treatment trial enrolling 100 SLE patients including replacements due to screen failures and withdrawals. If a patient drops out of the study before completion both arms, another patient may be enrolled so that up to 75 patients complete the study. They will be treated for 3 months with 45 mg daily pioglitazone or placebo, undergo an 8 week washout period, then undergo crossover to the other arm for 3 additional months. Throughout the study, functional, anatomical and blood biomarkers of vascular damage, atherosclerosis risk and SLE activity will be collected. Pioglitazone has been chosen over rosiglitazone because it appears to have a significantly better safety profile regarding CV effects and lipid profile alterations⁹³, based on our experience in the rheumatoid arthritis (RA) trial⁵ and the small pilot study published by

another group that showed improvement in some metabolic parameters in SLE⁹², as well as our preliminary data which indicate improvement of vasculogenesis by pioglitazone but not rosiglitazone⁹⁴ in human SLE. We also have significant experience using this drug due to the recently completed clinical trial in RA³. The dose and study time period have been selected based on pioglitazone's macrovascular protective effects⁷⁴ and to allow detection of meaningful changes in endothelial function and disease activity, respectively. This is also based on the dose and study time period used in the RA trial, which showed significant effects on arterial stiffness, metabolic parameters, inflammatory markers and RA disease activity⁵.

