10.4 Blinding, Packaging, Labeling and Storage

Study agent (15 mg pioglitazone or placebo) will be packaged in identical vials each containing 300 capsules. Both study agents will be blinded using identical-looking capsules prepared by a vetted vendor selected by the NIH Pharmaceutical Development Service (PDS). Each vial will be labeled with a treatment number specific to the subject. A 300 capsule (one vial) supply of study agent will be given to each subject at enrollment at the baseline visit and at month 5. The amount of study agent dispensed will be sufficient to last from baseline to month 3, and from month 5 to month 8. The randomization code will be provided by the Clinical Center Research Pharmacy, as mentioned above. Emergency unblinding will occur in the case of a serious adverse event (SAE) that is considered potentially secondary to the drug. Unblinding will be performed by PDS. Only the pharmacists will be unblinded throughout the trial. The subjects, the investigators, and the study site staff will remain blinded to study medication assignment during the entire study period. Compliance with study treatment and pill counts will be performed by the research nurse/study coordinator and this information will be provided to PDS as well.

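### Section 9.5.1 does not say whether a step-down to two capsules in period 1 carries into period 2; read literally, symptoms on placebo can cap the later pioglitazone dose, and only in placebo-first patients

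*Combined protocol and SAP*

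**What the plan says.** Section 8 summarises the intervention without qualification: "They will be treated for 3 months with 45 mg daily pioglitazone or placebo". Section 9.5.1 gives the operating detail. Titration belongs to the period: "The first week of each treatment arm, patients will take two 15 mg capsules of pioglitazone daily (30 mg total daily dose"), rising to three capsules (45 mg) if no significant side effects appear. The same schedule applies to placebo: "Subjects will be instructed to follow the same titration for the placebo arm". Patients are telephoned before the increase and again one to two weeks after it.

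The step-down follows in the same paragraph. Its trigger is "If 45 mg dose is not well tolerated but the 30 mg dose is well tolerated"; its consequence is that the "dose will be decreased back to 30 mg daily for duration of trial". The trigger makes no reference to which agent the capsules contain.

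Three other sections bear on the reading. Section 9.4 randomizes patients 1:1 to the two sequences. Section 10.2 treats the study as complete only after 8 months and both treatment arms. Section 10.4 keeps subjects, investigators and site staff blinded: "Only the pharmacists will be unblinded throughout the trial". The analysis model in Section 11 has treatment, period and baseline terms. It names no dose-level variable and no handling of patients held at two capsules.

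**The concern.** One sentence ties titration to the treatment arm. Another ties the step-down to the whole trial. After a step-down in period 1 they give different instructions at month 5, and two members of staff could act differently while each followed the protocol.

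This matters because the consequence is one-sided. If the step-down carries over, a placebo-first patient can receive two-thirds of the described pioglitazone dose because of symptoms that arose on placebo, without having taken three active capsules. Nothing equivalent happens to the active dose of a pioglitazone-first patient, whose pioglitazone period is already over. The treatment being estimated would then depend slightly on sequence, for a reason unrelated to the drug, and the planned analysis would not show how often this occurred.

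**Working it through.** The plan states no figure on this point, so there is none to reproduce. The check is a reading of the rule, followed by a rough estimate of size.

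**1. The two readings at month 5, for a patient who stepped down in period 1**

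| Sequence | Step-down occurred on | Period 2 if titration restarts | Period 2 if the step-down carries over |
|---|---|---|---|
| Placebo first | placebo capsules | 30 mg pioglitazone for a week, then 45 mg if no significant side effects | 30 mg pioglitazone throughout |
| Pioglitazone first | pioglitazone capsules | two, then three placebo capsules | two placebo capsules throughout |

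Only the placebo-first row has an active dose that depends on the reading. The asymmetry follows from the wording and needs no assumed rate. Because the site is blinded, the decision to step down cannot take account of what the capsules contain.

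**2. Inputs for size**

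- Dose reduction in an affected patient: 15/45 = 33%.
- Completers: up to 75 (Section 8). With 1:1 allocation, 75/2 = 37.5, roughly 38 placebo-first.
- Probability *q* that a patient steps down on placebo: not given anywhere, so an assumption. Table 2 (RA trial) offers two guides: edema on placebo 0/127, and at least one adverse event on placebo 23/127 = 18.1%.
- Exact 95% upper limit for 0/127: 1 − 0.025^(1/127) = 2.9%. Exact 95% interval for 23/127: 11.8% to 25.9%.

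**3. Expected number affected, if the step-down carries over**

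Expected number = *q* × 37.5. Share of all pioglitazone periods = *q*/2. If effect is proportional to dose (an assumption), the fall in mean treatment effect = (*q*/2) × (1/3).

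| *q* | Basis | Patients affected | Share of pioglitazone periods | Fall in mean effect |
|---|---|---|---|---|
| 0 | observed placebo edema | 0 | 0 | 0 |
| 2.9% | upper limit for placebo edema | 1.1 | 1.4% | 0.5% |
| 5% | assumed | 1.9 | 2.5% | 0.8% |
| 10% | assumed | 3.8 | 5.0% | 1.7% |
| 18.1% | any adverse event on placebo | 6.8 | 9.1% | 3.0% |

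Counting all 100 planned enrollees, 50 per sequence, gives 1.4 patients at 2.9% and 9.1 at 18.1%. The shares and percentage falls are unchanged.

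The lower rows are more relevant than the last. Section 9.5.1 describes the side effects of interest as mainly fluid retention, and most adverse events of any kind would not lead to a dropped capsule. Zero is not certain either: the telephone screen also asks about other side effects, and these are SLE rather than RA patients.

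**The case against.** The strongest defence is that this is a general rule with an exception, loosely worded. The authors may have meant the step-down to last for the rest of that treatment period, and on that reading the problem disappears. Section 8 is a design summary, so its plain 45 mg does not by itself contradict the detail in Section 9.5.1. The primary analysis is intent-to-treat, so dose reductions for tolerability belong to the regimen being compared. Some recording already exists: pill counts, drug accountability at months 3 and 8, and an action-taken field for each adverse event.

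Much of this stands. The intended meaning may well be the narrower one, and the number affected is small on any reasonable assumption. But no sentence limits the step-down to the period, and Section 10.2 counts both arms as the study. A cap set by symptoms on placebo is not a tolerability response to pioglitazone, so intent-to-treat does not settle it. Pill counts cannot separate a prescribed step-down from missed doses, and no table by sequence is planned.

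Three stronger readings are tempting and are not supported:

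- A reader might infer that pioglitazone-first patients are always offered 45 mg. They are not: the increase depends on the absence of significant side effects in week 1.
- A reader might infer that pioglitazone-first patients reduce only because of the drug, and so calculate a difference in mean active dose between sequences. Under blinding, symptoms unrelated to the drug can cause a step-down during the pioglitazone period in either sequence. The documents give no step-down rate for either period from which such a difference could be estimated.
- A reader might expect the effect to appear as a sequence or carryover signal in the Section 11 check. Nothing in the documents shows that, and a few patients at two-thirds dose among about 38 is weak ground for expecting it.

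**Conclusion.** The point holds as an unresolved conflict in the dosing instructions with a small, one-sided effect on the active dose. Followed literally, Section 9.5.1 lets symptoms on placebo capsules cap period-2 pioglitazone at 30 mg in placebo-first patients only, and no other section resolves it. The plausible size runs from no patients to about 1 of roughly 38 placebo-first completers on the edema figures, with about 7 as a ceiling. At that ceiling the mean treatment effect falls by about 3%.

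These figures assume that the step-down carries over, that RA-trial placebo rates are a fair guide to SLE patients, and that effect is proportional to dose. This is not a threat to the trial's conclusions. It is worth correcting because the protocol gives two instructions for one situation and because the correction is nearly free. No view is taken here on which dosing rule is right.

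**What to change.** Reconcile the two sentences in Section 9.5.1 so that one rule, chosen by the sponsor's clinicians, governs the capsule count in period 2 and states expressly whether a step-down in period 1 carries past the month 5 visit. Bring the Section 8 summary into line with it.

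Record the prescribed capsules per day in each period on the eCRF, separately from the pill count. In the analysis, report the proportion of patients at two capsules by treatment and by sequence.

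The cost is a sentence or two of protocol text, one eCRF field and one table. No patients, visits or procedures are added.
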